### 3.3. Exploratory Endpoint

Serum samples and peripheral blood mononuclear cells (PBMC) may be collected at Screening and Study Days 1, 8, 15, and 29, and Months 3 and 6 for potential new biomarkers predictive of efficacy as well as characterization of the DFU population response to treatment. Specific goals include: contribution to evaluation of safety and efficacy, evidence for repair and regeneration activity, and identification of universal pharmacodynamic biomarkers for PDA-002. Analysis of biological fluids and PBMCs will include the examination of research biomarkers as well as vascular and standard inflammatory markers. The analyses will be performed via polymerase chain reaction (PCR)-based evaluation of levels of messenger ribonucleic acid (mRNA), as well as proteomics-based assessment of protein levels in response to treatment. The analyses will not include any genetic testing of subjects.

## 4. OVERALL STUDY DESIGN

### 4.1. Study Design

This is a Phase 1, multicenter, open-label, dose-escalation study in subjects with PAD and DFU. The study will enroll up to 24 subjects. The study will utilize a 3 + 3 dose escalation design with 3 to 6 subjects enrolled into each of 4 dose cohorts. Subjects will be assigned to a dose cohort based on the order of entry into the study.

Four PDA-002 dose levels are planned in this study:

Dose Level 1:  $3 \times 10^6$  cells administered on Study Days 1 and 8.

Dose Level 2:  $10 \times 10^6$  cells administered on Study Days 1 and 8.

Dose Level 3:  $30 \times 10^6$  cells administered on Study Days 1 and 8.

Dose Level 4:  $100 \times 10^6$  cells administered on Study Days 1 and 8.

Initially, 3 subjects will begin dosing at the  $3 \times 10^6$  cells dose level. Progression to higher (or lower) PDA-002 dose levels will be based on the following criteria:

**Table 1: Dose Escalation Scheme**

Number of Dose-limiting Toxicities	Action Regarding Study Drug
If 0 out of 3 subjects experience a DLT during the first 14 days of follow-up (Day 15) at a given dose level:	Enroll 3 subjects at the next highest dose level (If at the $100 \times 10^6$ cells dose level, 3 additional subjects will be enrolled).
If 1 out of 3 subjects experience a DLT during the first 14 days of follow-up (Day 15) at a given dose level:	Enroll 3 additional subjects at the current dose level
If $\geq 2$ out of 3 subjects experience a DLT at a given dose level:	Enroll 3 subjects at the next lowest dose level a
If 3 additional subjects are enrolled at a given dose level:	
If 1 subject out of 6 subjects experiences a DLT during the first 14 days of follow-up (Day 15) at a given dose level:	Enroll 3 subjects at the next highest dose level (except if at the highest dose level of $100 \times 10^6$ cells).
If $\geq 2$ subjects out of 6 subjects experience a DLT during the first 14 days of follow-up (Day 15) at a given dose level:	Enroll 3 subjects at the next lowest dose level

Abbreviations: DLT = Dose-limiting toxicities; MTD= Maximum tolerated dose.

a If dose level 1 ( $3 \times 10^6$  cells) exceeds the MTD, a PDA-002 dose level of  $1 \times 10^6$  cells will be evaluated.

All subjects in a given dosing-cohort must complete 14 days of follow-up and the data reviewed by an internal Data Monitoring Committee (DMC), as detailed in Section 6.4) and approval given to dose escalate before accrual to the next dosing cohort can begin.

Subjects who discontinue from the study prior to the Study Day 15 assessments for reasons other than a dose-limiting toxicity (DLT) will be replaced. Subjects who experience a DLT should continue to complete all protocol assessments and will not be replaced.

The pattern of enrollment outlined in [Table 1](#) will continue until the MTD is determined or the highest planned dose level is tested. Six subjects must be treated at a given dose level before the MTD can be declared. The MTD is defined as the highest PDA-002 dose level for which the incidence of DLT is  $\leq 1$  out of 6 subjects. At any dose level, if 2 or more subjects experience a DLT within 14 days of dosing, that cohort will have exceeded the MTD. If a previous dose level was well tolerated and no subjects experienced DLT at that level, an intermediate dose level may be defined by protocol amendment.

[figure not shown]
Subjects will undergo screening evaluations to determine eligibility within 28 days of Study Day 1. Following Screening, subjects will be assigned to the appropriate cohort as outlined above and will receive IP. In the case of bilateral limb ulcers, the treated limb will be the limb that has the largest ulcer total surface area. During the treatment period, subjects will receive intramuscular (IM) injections of PDA-002 on Study Days 1 and 8. No more than 1 subject may begin treatment in any 48-hour period. During the follow-up period subjects will be evaluated on Study Days 15 and 29, and Months 3, 6, 9, 12, and 24. All subjects are to receive standard of care treatment in addition to IP. An interim analysis will be performed after the last subject completes 3 months of follow-up.

All subjects who receive any dose of PDA-002 will participate in the 24-month follow-up period. Refer to [Figure 2](#) in this section for the overall study visit design and Section 5, [Table 2](#), Table of Events for the scheduled visits and assessments.

Primary safety assessments, including AE reporting, physical examinations, vital sign measurements, ECG, injection site assessments, MRI or CT scan results, retinal examination results, concomitant medications, and clinical laboratory evaluations will be performed at scheduled visits throughout the study.

Efficacy analyses will include assessment of changes in the ABI and/or TBI. Additional assessments include evaluation of changes in Rutherford Criteria, number; extent and size of ulcers; leg rest pain score using a VAS, incidence of hospitalization (all cause); overall survival at 24 months; and the time to first occurrence of major amputation (above the ankle) of treated leg, all-cause mortality, doubling of ulcer total surface area from baseline, or de novo gangrene (see Section 3).

**Figure 2: Overall Study Design**

## 4.2. Study Design Rationale

This is the first study that will evaluate the safety and potential efficacy of IM injection of PDA-002 in type 1 and type 2 diabetic subjects with PAD and DFU. There are limited options available for DFU subjects when conservative treatment methods and vascular surgery have not and/or are not expected to provide benefit. Debridement of necrotic tissue and callus is always indicated in the treatment of DFU and is allowed in this study. Patients with infections need to be treated and have the infection resolved prior to continuation of medical management (Frykberg, 2006). There is a current medical need for treatments that could restore blood flow to the lower extremities and therefore aid in the healing of diabetic foot ulcers. Current results from the rat hind limb ischemia model show that stem cells isolated from human placenta (formulated for IM injection as PDA-002) have potential clinical use in tissue repair through increasing angiogenesis and promoting muscle regeneration (see Investigator's Brochure, Section 3.1.2.1.2). Furthermore, these PDA-002 cells implanted in a mouse model of chronic hind limb ischemia improved blood perfusion and limb functional recovery.

The use of a 3+3 dose escalating tolerability algorithm with strict DLT criteria will allow detection of significant toxicity in this first trial with PDA-002 given by IM injection. With regard to route of administration, IM administration of the cells is expected to reduce the potential risk of vascular complications seen with direct IV administration of the PDA-001 cells. After IM administration in animal models, there was no evidence of distribution to the vascular compartment and PDA-002 cells were detected only at the site of administration and draining lymph nodes. Care will be taken to avoid systemic injection of cells. It is unlikely that detectable numbers of PDA-002 cells will enter the systemic circulation.

To further reduce the risk of vascular complications, this study is including subjects with PAD (with ankle-brachial index > 0.6 and ≤ 0.9 or toe-brachial index > 0.35 and ≤ 0.7) and DFU. Men and women with an ankle-brachial index of > 0.6 have lower 10-year-total mortality,

cardiovascular mortality, and major coronary event rates than subjects with an ankle-brachial index  $< 0.6$  (Chronic Limb Ischemia [CLI]) (Fowkes, 2008). Subjects can have stable angina (Canadian Cardiovascular Society [CCS] Class I-II angina), but must not have a history of malignant ventricular arrhythmia, CCS Class III-IV angina pectoris, myocardial infarction/PCI (percutaneous coronary intervention)/CABG (coronary artery bypass graft) in the preceding 6 months, have planned coronary revascularization in the next 3 months, or transient ischemic attack/cerebrovascular accident in the preceding 6 months. Subjects may not have New York Heart Association [NYHA] Stage III or IV congestive heart failure or uncontrolled hypercoagulation, diabetes or blood pressure (see Section 7).

The dose levels for this study are based, in part upon the pre-clinical in vitro and in vivo data. Intramuscular administration of PDA-002 cells to rats at doses up to  $12 \times 10^6$ /rat were well tolerated. There were no deaths, adverse clinical observations, or histopathologic findings related to cell dosing in tissues examined. The presence of human DNA was detected only on Day 1 and only at the injection site. PDA-002 cells at doses as low as 1000 and 3000 cells were active in improving blood flow in mouse and rat HLI models, respectively. The dose levels planned for this study will range from  $3 \times 10^6$  to  $100 \times 10^6$  cells (less than 25% of the highest equivalent dose tested in rats). All dose levels of PDA-002 are expected to be well tolerated based on the in vitro and ex vivo data. This study will not have adequate numbers of patients to determine benefit unless dramatic responses are observed. The objectives of this study are to define an MTD(primary) for further study in Phase 2, and assess safety and tolerability as well as initiating exploration of potential efficacy, mechanisms of action and potential predictive biomarkers for PDA-002.

[figure not shown]
### **4.3. Study Duration**

[figure not shown]
The study consists of a 0 to 28 day screening/baseline period followed by a 7-day treatment period (treatment on Study Days 1 and 8) plus a 24-month follow-up period.

## 5. TABLE OF EVENTS

**Table 2:** Table of Events (Continued)

**Table 2:** Table of Events (Continued)

**Table 2.** Table of Events (Continued)

[REDACTED]	
------------	--

## 6. PROCEDURES

The study is divided into 3 periods: Screening/baseline, Treatment and Follow-up with associated evaluations and procedures that must be performed at specific timepoints. The Screening/Baseline Period is defined as the 28 days before administration of IP, during which subjects are evaluated for eligibility. The Treatment Period consists of Study Days 1 and 8 when the IP is administered. The Follow-up Period begins after Study Day 8 and is completed at Month 24. An interim analysis of safety and efficacy will be performed after the last subject in the study completes 3 months of follow-up. All subjects should be followed for the full 24 months regardless of clinical response.

All subjects are to receive standard of care for DFU in addition to IP.

The schedule of study procedures is shown in the Table of Events ([Table 2](#)) and the Study Design Schema ([Figure 2](#)). A description of specific study procedures is provided in the following subsections.

### 6.1. Study Entry, Screening and Baseline Period

#### **Explain Study and Obtain Written Informed Consent**

Before or at Visit 1, the Investigator or designee will explain the study to the subject, answer all of his or her questions and obtain written informed consent and Health Insurance Portability Accountability Act (HIPAA) authorization before performing any study-related procedures. Procedures conducted as part of standard of care performed prior to signing of the informed consent must be documented.

A copy of the informed consent will be given to the subject.

#### **Demographic and Medical History Including Baseline Signs and Symptoms**

Demographics and medical history will be obtained by the Investigator or designee during Screening. Demographics will include date of birth, gender, ethnicity, and race. Medical history should include history relevant to the study indication, psychiatric history, current medical conditions, height and weight, information on all prior therapies related to the study indication, and any allergic conditions. A more detailed medical history to identify patients at high risk of developing new tumors or having prior tumors recur will be done. A physical examination, including collection of vital signs, height and weight, will be performed. Baseline signs and symptoms will be recorded as medical history. Prior therapies should include all medications (including contraceptive measures and over-the-counter products) and therapies used within 30 days prior to the Screening visit. Rutherford Criteria, Wagner Grading Scale for foot lesions, measurement/assessment and photography of ulcers, ABI and TBI, and leg rest pain score using a VAS will be assessed. An MRI or CT of the chest, abdomen and pelvis, an ECG, and a retinal examination will also be completed.

#### **Review Inclusion/Exclusion Criteria Including Concomitant Medications**

Prior to treatment with IP all subjects will be screened for study eligibility. Any concomitant medications the subject is currently taking will be recorded and assessed for eligibility ([Section 9](#)). Samples for serum chemistry, hematology, urinalysis, lipids and fatty acid analysis,

CECs, immunological and inflammation assessments, hemoglobin A1c, pregnancy test (only in females of childbearing potential), urinary cotinine, troponin I, coagulation assessments, and exploratory biomarkers will be collected. If the subject meets all the study eligibility criteria (Section 7), the subject will be assigned to a cohort as outlined in Section 4.1 and scheduled for dosing with IP.

If the subject does not meet all of the study eligibility criteria, the subject will be considered a screen failure and will be discontinued and replaced.

## **6.2. Treatment**

Subjects will be treated with IP administered IM on Study Days 1 and 8. In the case of bilateral limb ulcers, the treated limb will be the limb that has the largest ulcer total surface area. Prior to dosing with the IP, subjects will undergo a physical examination, including weight and vital signs, an ECG, and a review of concomitant medications and procedures. Blood samples for serum chemistry, hematology, troponin I, lipids and fatty acid analysis, immunological/inflammation assessments, hemoglobin A1c (Study Day 1 only), tryptase, histamine, CECs, exploratory biomarkers, and coagulation assessments should be drawn on the day of treatment prior to dosing with the IP. A urinalysis, a urine pregnancy test in females of child bearing potential, and a urinary cotinine test should also be performed prior to dosing with IP. Assessment of Rutherford Criteria, Wagner Grading Scale for foot lesions, measurement/assessment and photographs of ulcers, and determination of ABI, TBI, and leg rest pain score (VAS), should be performed on Study Days 1 and 8.

Investigational product will be thawed and diluted as per the pharmacy manual. Thawing of the IP should not begin until it is confirmed that the subject meets all eligibility criteria. The injections of IP (PDA-002) will be administered as described in Section 8.2. Vital signs (including heart rate, respiration, resting systolic and diastolic blood pressure, body temperature, and pulse oximetry) will be monitored prior to starting the injections and every 15 minutes for a minimum of 2 hours after completion of the injections. Blood samples for tryptase and histamine, coagulation assessments, CECs, and exploratory biomarkers will be collected approximately 2 hours after the injections have been completed. The injections must be completed within 4 hours of IP thaw time. Injection sites will be assessed. See Section 6.4.4 regarding injection site reactions.

## **6.3. Efficacy Procedures**

### **6.3.1. Rutherford Criteria**

Limbs will be assessed using the Rutherford Criteria (Rutherford Classification of Chronic Limb Ischemia, [Appendix B](#)) during Screening, on Study Days 1, 8, 15, and 29, Months 3, 6, 9, 12, and 24, and at early termination. Subjects who improve by at least one numeric category will be defined as improved, while subjects who fail to improve or deteriorate by at least one category will be defined as non-responsive.

### **6.3.2. Ulcer Assessment**

Ulcers will be graded using the Wagner Grading Scale ([Appendix A](#)) and will also be assessed using the E-Z graph system [Appendix E](#)). In addition, photographs will be taken of the ulcers

(Appendix F). The number, extent, and size of ulcers, including summation of the products of the long x short axis for all ulcers measured in centimeters squared plus the ulcer depth will be captured. Ulcer healing is defined as skin closure without drainage or need for dressing. Limbs will also be assessed for gangrene. Ulcers will be assessed at Screening, on Study Days 1, 8, 15, and 29, Months 3, 6, 9, 12, and 24, and at early termination. Information for ulcers assessed at non-scheduled visits will also be collected.

### **6.3.3. Ankle-Brachial Index and Toe-Brachial Index**

The ABI and TBI should be obtained bilaterally by measuring both the posterior tibial and dorsalis pedis arteries for the ABI and the first or second toe digital artery for the TBI dividing the systolic blood pressure at the ankle or toe by the systolic blood pressures (Doppler technique) in the arm). ABI and TBI will be assessed during Screening, on Study Days 1 and 8 prior to administration of PDA-002, on Study Days 15 and 29, Months 3, 6, 9, 12, and 24, and at early termination.

### **6.3.4. Pain**

Leg rest pain score will be assessed using a visual analog scale (VAS) (Appendix D) during Screening, on Study Days 1 and 8 prior to administration of PDA-002, on Study Days 15 and 29, Months 3, 6, 9, 12, and 24, and at early termination.

### **6.3.5. Other Clinical Assessments**

Subjects will be assessed for amputation status and need for hospitalization. Major amputation is defined as that occurring above the ankle. The reason for amputation will be assessed and documented (pain, gangrene, disease progression, local infection, systemic infection, failure to heal, osteomyelitis, other) on the electronic case report form (eCRF).

## **6.4. Safety**

Safety will be assessed by an ongoing review of clinical laboratory tests (hematology, serum chemistry, lipids, fatty acids, coagulation, troponin I, pregnancy, urinalysis, immunological/inflammation), physical examination results, vital sign measurements, 12-lead electrocardiogram (ECG), evaluations by MRI or CT scans of the chest, abdomen and pelvis, retinal exams, use of concomitant medications/procedures, and the incidence and severity of injection site and injection-related reactions (including tryptase and histamine) and treatment-emergent AEs.

### **6.4.1. Dose-Limiting Toxicity**

A DLT is defined as a Grade 2 toxicity not resolving within 14 days suspected to be related to the IP or any toxicity  $\geq$  Grade 3 suspected to be related to the IP.

In the event that 2 separate subjects within a dosing cohort experience a DLT, the events will be forwarded to the internal DMC for review and confirmation as to whether or not the MTD has been exceeded. If the MTD is confirmed by the internal DMC, no further IP administration will occur within that dose level or at any higher dose level. An intermediate dose may be defined by protocol amendment.

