### **Dose-limiting Toxicity**

A DLT is defined as a Grade 2 toxicity not resolving within 14 days suspected to be related to IP or any  $\geq$  Grade 3 toxicity suspected to be related to IP.

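### Counted from onset, a Grade 2 reaction to the second dose cannot qualify as a DLT by the earliest Day 15 review, and no visible rule covers an event still open when escalation is decided

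*Protocol*

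**What the plan says.** Section 6.4.1 of the Protocol gives two routes to a DLT. One is any related toxicity of Grade 3 or higher. The other is the Grade 2 limb: "A DLT is defined as a Grade 2 toxicity not resolving within 14 days suspected to be related to the IP". The synopsis has the same rule ("A DLT is defined as a Grade 2 toxicity not resolving within 14 days suspected to be related to IP"), and SAP Section 11.1 repeats it. None of the three says on which day the 14 days begin, or whether the DLT is dated by its onset or by the day it meets the criterion.

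Doses are given on Days 1 and 8. In Table 1 (Section 4.1) the row that allows escalation reads "If 0 out of 3 subjects experience a DLT during the first 14 days of follow-up (Day 15) at a given dose level". The 1/3 row uses the same window and calls for three more subjects at the current dose. At 100 × 10^6 cells the 0/3 row also expands ("cells dose level, 3 additional subjects will be enrolled"). The row for two or more DLTs carries no day limit: "out of 3 subjects experience a DLT at a given dose level".

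Under Section 6.4.2 the internal DMC meets once a cohort has finished dosing and its Day 15 assessments. It must approve escalation, and it decides on the AE and clinical data available. Section 6.4.1 adds a referral: "In the event that 2 separate subjects within a dosing cohort experience a DLT, the events will be forwarded to the internal DMC". Section 4.1 staggers entry: "No more than 1 subject may begin treatment in any 48-hour period".

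**The concern.** The definition needs 14 days of persistence, and the decision is taken 14 days after the first dose. If persistence is counted from onset, almost any Grade 2 event that starts after the first dosing day is still undetermined when its subject reaches Day 15, including every reaction to the second dose. Below the top dose the difference between 0/3 and 1/3 is the difference between escalating and expanding, so one open event can decide the action.

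The visible text does not say whether an open related Grade 2 event counts as a DLT, is ignored or delays the decision. SAP Section 11.1 imputes only a missing grade or a missing relationship. This matters because Section 4.2 rests the safety of the first intramuscular trial on the rule: "The use of a 3+3 dose escalating tolerability algorithm with strict DLT criteria will allow detection of significant toxicity in this first trial".

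**Working it through.** **Inputs.** Doses on Days 1 and 8, window to Day 15, starts at least 48 hours apart, and dose levels of 3, 10, 30 and 100 × 10^6 cells (Section 4.1). Grade 2 persistence of 14 days (Section 6.4.1). No DLT rates or onset times are given in the documents.

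**1. The plan's own window.** Day 1 + 14 = Day 15, which agrees with Table 1.

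**2. When an onset can be classified.** The earliest day is onset + 14, or onset + 13 if the onset day counts.
- Day 1 onset: Day 15 (14)
- Day 2 onset: Day 16 (15)
- Day 8 onset: Day 22 (21)
- Day 15 onset: Day 29 (28)

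By a subject's own Day 15, only Day 1 onsets (Days 1 and 2 if the onset day counts) can be classified. The other 14 (13) of the 15 possible onset days cannot.

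**3. The earliest cohort review.** With starts at 0, 2 and 4 days, the three subjects are at Days 19, 17 and 15 when the third completes follow-up. Subtracting 14 gives latest classifiable onsets of Days 5, 3 and 1; subtracting 13 gives Days 6, 4 and 2. All precede Day 8, so no second-dose reaction can count through the Grade 2 limb at that review. With slower accrual or a later review, a Day 8 onset becomes classifiable in any subject at least 7 (6) days past Day 15.

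**4. Three readings of the same text.**
- Clock from onset, DLT dated by onset: a cohort at 0/3 on review can later become 1/3.
- 14 days means the window ending on Day 15: any related Grade 2 event open at Day 15 is a DLT, and the gap closes.
- Clock from onset, DLT dated when the criterion is met: late-maturing events fall outside the Day 15 rows and are never counted there.

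**5. What is exposed on the first reading.** Dose steps are 10/3 = 3.3, 30/10 = 3.0 and 100/30 = 3.3. A Day 8 onset in the last subject qualifies 22 − 15 = 7 days after the earliest review. With same-day approval and starts at 0, 2 and 4 days, all three next-level subjects could have had a first dose by then. This is the fastest possible case.

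**6. Illustration of size.** Let t be the true DLT rate and u the share of DLTs still open at review; both are assumed.
- Chance that 0/3 at review later becomes exactly 1/3: A = 3tu(1 − t)^2.
- Chance that the level would then have failed expansion (at least one DLT in three more subjects): B = 1 − (1 − t)^3.
- Chance of both: A × B.

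| t | B | u | A | A × B |
|---|---|---|---|---|
| 0.33 | 1 − 0.301 = 0.699 | 0.10 | 0.044 | 0.031 |
| 0.33 | 0.699 | 0.25 | 0.111 | 0.078 |
| 0.33 | 0.699 | 0.50 | 0.222 | 0.155 |
| 0.25 | 1 − 0.422 = 0.578 | 0.10 | 0.042 | 0.024 |
| 0.25 | 0.578 | 0.25 | 0.105 | 0.061 |
| 0.25 | 0.578 | 0.50 | 0.211 | 0.122 |

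Column A alone overstates the harm, because a level that expands from 1/3 can still pass, with probability 30% at t = 0.33 and 42% at t = 0.25.

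**The case against.** The strongest reply is that the gap depends on a reading the text does not fix. Elsewhere in the dose-finding rules 14 days is a fixed window: Table 1, the MTD sentence in Section 4.1 and the stopping rule in Section 6.4.3 all use it that way. Read so, an open related Grade 2 event at Day 15 is already a DLT. This stands as a real alternative. It does not remove the need for a clarification, since the three readings give different counts from the same data, and under this one a Grade 2 event that began on Day 14 would be dose-limiting a day later.

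Several safeguards also stand:
- Escalation is never automatic. The DMC must approve it, reviews safety data on an ongoing basis (Section 6.4.2), and could wait or count open events as DLTs. Its charter is a separate document not seen here, and the SAP's AE date rules are redacted.
- Events in two or more subjects are partly covered by the untimed Table 1 row, the two-DLT referral and the stopping rules, one of which covers Grade 2 or higher allergic reactions with no duration condition. None of these reaches a single open event.
- The Grade 3 or higher limb is unaffected. At 100 × 10^6 cells, 0/3 and 1/3 lead to the same action.

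A reader might infer that the MTD itself will be wrong. The documents do not support that. Six subjects must be treated at a level before it can be declared the MTD, so a level passed at 0/3 cannot be named without the expansion it skipped. At the six-subject review the first three are at Day 33 or later (15 + 4 + 14), when all their onsets through Day 15 are settled.

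**Conclusion.** The point holds as a conditional gap that should be fixed. The start of the Grade 2 clock and the dating of the DLT are undefined. With both taken from onset, the plan as written permits escalation below the top dose where the completed count would call for expansion. The consequence is temporary over-exposure of next-level subjects to a 3.0 to 3.3-fold dose.

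Confidence is high that the text is undefined and that the day arithmetic is right. It is lower that the scenario would occur, because that also requires the DMC to approve escalation with the event open.

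The true size is unknown. The illustrative 3%, 8% and 16% (33% rate) and 2%, 6% and 12% (25% rate) apply one open share to all three subjects, although earlier subjects have longer follow-up. Grade 3 or higher DLTs are never pending, so a 50% share would need half of all DLTs to be late, persistent Grade 2 events, and nothing in the documents supports that. If the DMC counts open events as DLTs, the excess does not arise.

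**What to change.** In the synopsis DLT definition, Section 6.4.1, Table 1 and SAP Section 11.1, state that the Grade 2 14-day clock runs from onset and that the DLT is attributed to its onset day, with onsets through Day 15 counting. Then add:

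> *A related Grade 2 toxicity unresolved at the Day 15 review and present for less than 14 days is DLT status undetermined; if counting it as a DLT would change the Table 1 action, that action is held until the event resolves or reaches 14 days.*

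Align the DLT window in the stopping rule (synopsis and Section 6.4.3). Confirm each cohort's count from the AE start and stop dates already recorded under Section 11.2.4 and from the existing Day 29 visit, which completes 14 days for onsets through Day 15. Send any change to the DMC; the enrollment hold in Section 6.4.2 can carry the pause.

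The cost is amendment wording, with no new visit or data item. The downside is an occasional cohort delay of up to about 14 days (Day 29 − Day 15), only when a pending event would change the action.
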